The application of these techniques within the project of "Identification of a possible rehabilitative protocol through the use of direct current brain stimulation (tDCS) in patients affected by cerebellar ataxia of neurodegenerative origin." Approved by this Ethics Committee allowed to identify a clinical improvement also in patients affected by cerebellar ataxia subjected to cerebral transcranial electrical stimulation, also supported by neurophysiology data (Benussi et al., 2015a; Benussi et al., 2017).

This application could also be applied in amyotrophic lateral sclerosis (ALS), a progressive chronic neurodegenerative pathology in which there is an irreversible degeneration of the first and second motoneurons at the level of the motor cortex and of the spinal cord, respectively. ALS is characterized by muscle stiffness, muscle contractions and gradual progressive weakness secondary to muscular atrophy. This results in difficulty in speech, swallowing and, finally, breathing (Salameh et al., 2015). At present, there is no known cure for ALS. One drug, riluzole, can extend life expectancy by about two or three months (Miller et al., 2012).

For this purpose, cortico-spinal transcranial electrical stimulation techniques have been developed, in which a simultaneous stimulation of the cerebral cortex (in this case in the area of the scalp corresponding to the motor cortex of both sides) and of the spinal cord (in this case in the area of the back corresponding to the dorsal-lumbar spinal cord) is applied (Fiocchi et al., 2016; Parazzini et al., 2014).

In order to evaluate an effect of tDCS on the progression of the pathology, some transcranial magnetic stimulation techniques (TMS) will be used in addition to the clinical and life quality scales. In fact, TMS has been widely used in the study of some neurodegenerative diseases, in particular in Parkinson's disease and in dementia due to Alzheimer's disease. Over the years, numerous TMS protocols have been developed to obtain information on neurophysiological parameters with the aim of investigating both the pathogenesis and the evolution of some neurodegenerative diseases (Benussi et al., 2015b).

Short-interval intracortical inhibition (SICI) is currently used to investigate intracortical inhibitory circuits. From neuropharmacology studies, it has been hypothesized that SICI is dependent on the activity of GABA_A receptors (Kujirai et al.,

CLINICA NEUROLOGICA - UNIVERSITA' DEGLI STUDI DI BRESCIA
UO Neurologia 2 - AZIENDA SOCIO SANITARIA TERRITORIALE degli SPEDALI CIVILI DI BRESCIA

Direttore: [name]

1993). In this way, alterations of the intracortical inhibitory circuits have been identified in many neurological diseases, in particular in dystonia and in parkinsonism. The study of intracortical facilitation (ICF) is used to investigate the combined effect of secondary facilitation on inhibitory and excitatory mechanisms mediated by GABA_A and NMDA receptors respectively (Ziemann et al. 1998).

In particular, in patients suffering from ALS, a deficiency of SICI and ICF has been observed, due to an imbalance in the mechanisms of inhibition and cortical facilitation mediated by GABAergic and glutamatergic interneurons (Menon et al., 2015). Based on these premises, treatment with tDCS is proposed in patients with ALS.

TARGETS:

The aim of the study is to evaluate the long-term effects of tDCS on clinical, biological and neurophysiological parameters in patients with ALS.

In particular, the clinical and quality of life scales currently used in clinical trials on ALS will be used (ALSFRS-R, ALSAQ-40, CBI, EQ-5D-5L, muscle strength assessed with the MRC scale). Moreover, SICI and ICF protocols will be evaluated through TMS.

PROCEDURES:

Subjects enrolled at the Neurological Clinic will be enrolled with the diagnosis of probable ALS, laboratory-supported, or defined according to the current clinical criteria (World Federation of Neurology Revised El Escorial criteria - Brooks et al., 2000).

Subjects will sign an informed consent and will be subjected to a neurological clinical evaluation using the clinical and quality of life scales currently used in clinical trials on ALS (ALSFRS-R, ALSAQ-40, CBI, EQ-5D -5L, muscle strength evaluated with the MRC scale in different muscle groups).

Clinical assessment: Neuromuscular impairment will be quantified by the five-point MRC scale megascore (shoulder abductors, elbow flexors and extensors, wrist flexors, thumb opponent, hip flexors, knee flexors and extensors, and ankle dorsiflexors and extensors on both sides for a total of 100). Good reliability and reproducibility for manual muscle testing in patients with ALS have previously been shown.

Clinical status will be evaluated with the ALSFRS-R, quality of life with the amyotrophic lateral sclerosis assessment questionnaire-40-item scale (ALSAQ-40), EQ-5D-5L and EQ-VAS, while caregiver burden will be evaluated with the caregiver burden inventory (CBI).

CLINICA NEUROLOGICA - UNIVERSITA' DEGLI STUDI DI BRESCIA
UO Neurologia 2 - AZIENDA SOCIO SANITARIA TERRITORIALE degli SPEDALI CIVILI DI BRESCIA

Direttore: [name]

Through the use of TMS techniques, the effects of tDCS on neurophysiological parameters will be evaluated, in particular SICI and ICF.

Transcranial Magnetic Stimulation assessment: TMS will be performed with a figure-of-eight coil (each loop diameter 70 mm) connected to a Magstim Bistim2 system (Magstim Company, Oxford, UK). Motor evoked potentials (MEPs) will be recorded from the right first dorsal interosseous muscle (FDI) through surface Ag/AgCl electrodes placed in a belly-tendon montage and acquired using a Biopac MP-150 electromyograph (BIOPAC Systems Inc., Santa Barbara, CA, USA).

The TMS coil will be held tangentially over the scalp region corresponding to the primary hand motor area contralateral to the target muscle, with the coil handle pointed 45° posteriorly and laterally to the sagittal plane. The motor hot spot will be defined as the location where TMS consistently produced the largest MEP size at 120% of the resting motor threshold (rMT) in the target muscle and was marked with a felt tip pen on the scalp to ensure constant placement of the coil throughout the experiment. Resting motor threshold (rMT) will be defined as the minimal stimulus intensity needed to produce MEPs with an amplitude of at least 50 μ V in 5 out of 10 consecutive trials during complete muscle relaxation, which will be controlled by visually checking the absence of EMG activity at high-gain amplification.

SICI and ICF will be studied at rest via a paired-pulse paradigm, delivered in a conditioning-test design, as previously reported. Briefly, the conditioning stimulus (CS) will be set at an intensity of 70% of the rMT, while the test stimulus (TS) will be adjusted to evoke a MEP approximately 1 mV peak-to-peak in the relaxed FDI. Different interstimulus intervals (ISIs) between the CS and TS will be employed to investigate preferentially both SICI (1, 2, 3 ms) and ICF (7, 10, 15 ms).

Ten stimuli will be delivered for each ISI and fourteen control MEPs in response to the TS alone will be recorded, for each paradigm, in all participants in a pseudorandomized sequence. The amplitude of the conditioning MEPs will be expressed as a ratio of the mean unconditioned response. The inter trial interval will be set at 5 sec ($\pm 10\%$). All protocols will be performed in a randomized order in all participants. Throughout the experiment, complete muscle relaxation will be monitored by audio-visual feedback where appropriate.

All clinical and, neurophysiological evaluations will be performed at baseline (T0), after 10 tDCS applications i.e. at two weeks (T1), at two months (T2) and at six months (T3).

After the first evaluation (T0), the patients will be divided into two groups randomly. The first group will undergo a tDCS stimulation protocol, while the second group will undergo a placebo (sham) treatment. tDCS will be delivered by a battery-driven

CLINICA NEUROLOGICA - UNIVERSITA' DEGLI STUDI DI BRESCIA
UO Neurologia 2 - AZIENDA SOCIO SANITARIA TERRITORIALE degli SPEDALI CIVILI DI BRESCIA

Direttore: [name]

constant current stimulator (HDCstim, Newronika, Milan, Italy) through a pair of saline-soaked (0.9% NaCl) surface sponge electrodes. The anodes will be placed on the scalp over the motor cortex area and the cathode over the spinal cervical enlargement (over C6) (see Fig. 1B). The electrodes will be secured using elastic gauzes and an electroconductive gel will be applied to electrodes to reduce contact impedance (<5 kΩ for all sessions). During real stimulation a constant current of 2 mA per each anodal electrode (4.0×6.5 cm², current density 0.077 mA/cm²) and 4 mA per cathodal spinal electrode (5.0×7.5 cm², current density 0.107 mA/cm²) will be applied for 20 minutes. For the sham condition, the electrode placement will be the same, but the electric current will be ramped-down 5 seconds after the beginning of the stimulation to make this condition indistinguishable from the experimental stimulation. To detect differences in the perception of the stimulation, patients will be asked whether they thought they were receiving real or sham stimulation at the end of the two-weeks' treatment.

INCLUSION CRITERIA for patients:

- Male or female patients diagnosed with probable ALS, laboratory-supported, or defined according to current clinical criteria (World Federation of Neurology Revised El Escorial criteria - Brooks et al., 2000).
- Age over 18 years;
- Disease duration ≤ 48 months;
- Score ≥ 2 at the item "swallowing" of the ALS Functional Rating Scale-Revised (ALSFRS-R);
- Score ≥ 1 at the item "walking" of the ALSFRS-R;
- Score ≥ 1 at the item "respiratory insufficiency" of the ALSFRS-R
- Signature of informed consent.

EXCLUSION CRITERIA for patients:

- Motor neuron diseases other than ALS;
- Diagnosis of dementia according to current clinical criteria;
- Severe head trauma in the past;
- Persons carrying static electrical stimulators (e.g. cardiac stimulators, nerve stimulators, auditory implants) that would not work or would be damaged by the magnetic field;
- Persons carrying special metallic foreign bodies (e.g. splinters, some prostheses, screws and nails) that could move if placed inside the magnetic field;
- People with a history of epilepsy or seizures;

CLINICA NEUROLOGICA - UNIVERSITA' DEGLI STUDI DI BRESCIA
UO Neurologia 2 - AZIENDA SOCIO SANITARIA TERRITORIALE degli SPEDALI CIVILI DI BRESCIA

Direttore: [name]

- History of ischemic stroke or hemorrhage;
- Severe comorbidity
- Given that the effects of TMS on the developing fetus are not known, pregnant women will be excluded from the study.

STUDY DESIGN:

This is a non-pharmacological, randomized double-blind controlled clinical trial. This study does not present sub studies. Patients will be randomized into two groups: each group will receive anodal bilateral motor cortex tDCS and cathodal spinal tDCS (real tDCS) or sham stimulation for 5 days/week for 2 weeks, in a 2:1 ratio respectively.

END POINTS:

The long-term effect of tDCS on clinical parameters (ALSFRS-R, ALSAQ-40, CBI, EQ-5D-5L, muscle strength assessed with the MRC scale in different muscle districts), and neurophysiological measures (SICI and ICF).

For efficacy analyses, the primary end point will be the defined as change from baseline in global MRC scores. Secondary end points will be defined as changes from baseline in the ALSFRS-R, ALSAQ-40, EQ-5D-5L, EQ-VAS, CBI and intracortical connectivity (SICI and ICF).

STATISTICAL PLAN:

Parametric analysis (t test) will be used to compare the demographic variables (e.g. age, duration of illness, education) of the various groups at the baseline. A p -value <0.05 will be considered significant.

In order to estimate the sample size, in order to obtain a significant difference in the primary outcome (Global MRC Score), we performed a "power analysis" based on the effects observed in a small group of patients (pilot study). The "effect size" $f(V)$ was calculated by direct method. Taking into account from previous observations a "partial $\eta^2 = 0.31$, equal to an "effect size" $f(V) = 0.67$ and, considering alpha = 0.05 and the power (1- β) = 0.80, considering a variable as covariate, the sample size expected for two patient groups (real and sham) is 25 total subjects using a repeated-measure ANCOVA study. The proposed sample size of 30 patients should be adequate to achieve the main objective of the study and would allow monitoring for confounding factors or drop-out patients.

Considering the unneglectable number of drop-out patients, that characterize most trials in ALS, we performed intention-to-treat and per-protocol analysis to reduce any bias due to the possible unbalanced drop-out rates between treatment groups. For

patients with missing values, data were assigned using mixed effects models for repeated measures without any ad hoc imputation.

To assess the effect of tDCS treatment on clinical scores over time, we will use a two-way repeated measure ANCOVA with TIME (T0, T1, T2 and T3) as within-subject factors and TREATMENT (sham vs real stimulation) as between-subjects factor, and the baseline values of each score as covariate, to reduce possible effects of baseline impairment on clinical score changes over time.

To assess the effect of tDCS treatment on TMS parameters we will use a two-way mixed ANOVA with TIME (T0, T1, T2 and T3) as within-subject factors and TREATMENT (sham vs real stimulation) as between-subjects factor.

When a significant main effect was reached, *post hoc* tests with Bonferroni correction for multiple comparisons will be conducted to analyze group-differences at respective time points. Mauchly's test will be used to assess for assumption of sphericity, while Greenhouse-Geisser epsilon determination will be used to correct in case of sphericity violation. Spearman's rank-order correlations will be used to assess associations between the improvement in clinical scores and neurophysiological parameters. Statistical analyses will be performed using SPSS version 21 (SPSS, Inc., Chicago, IL, USA).

ETHICAL CONSIDERATIONS (RISK-BENEFIT):

tDCS is a non-invasive, low cost and simple non-invasive brain stimulation method that is having an increasing diffusion and an increasingly numerous spectra of potential therapeutic applications such as, for example, post-stroke rehabilitation, depression and pain, which have already been established. Its effectiveness in modulating the excitability of the motor cortex in humans has been demonstrated (Nitsche et al., 2005). We therefore hypothesize that tDCS can have a positive effect on the clinical and quality of life scales, and restoration of neurophysiological parameters.

Literature data show that the application of the method according to the current safety guidelines (Iyer et al., 2005; Nitsche et al., 2003; Bikson et al., 2016) has little relevant side effects, among which mild tingling sensation during or after stimulation, moderate fatigue, mild itching sensation at the electrode sites, mild burning or pain, headache, nervousness, nausea, blistering at the electrode application points in rarer cases.

As for the TMS method, it is a non-invasive brain stimulation that allows the study of neurophysiological parameters that can provide information on the pathophysiological mechanisms involved in neurodegenerative diseases.

Literature data show that the application of the method according to the current safety guidelines has minor side effects: a certain number of subjects participating in TMS

CLINICA NEUROLOGICA - UNIVERSITA' DEGLI STUDI DI BRESCIA
UO Neurologia 2 - AZIENDA SOCIO SANITARIA TERRITORIALE degli SPEDALI CIVILI DI BRESCIA

Direttore: [name]

experiments (up to 20%) suffer from headaches or backaches, due to likely to an excessive muscle tension and a stiff position of the head and / or neck during TMS application. These effects are temporary and, in most cases, do not require any treatment.

With the parameters that we will use in this study, epileptic seizures have never been reported (Rossi et al., 2009). If an epileptic seizure occurs, this would occur during TMS, not later. However, this is an extremely rare complication. To prevent this, all TMS sessions will be performed in the presence of a neurologist and by personnel trained to give first aid and to immediately recognize the first signs of epileptic seizures. In addition, all TMS sessions will be carried out within the Neurology Unit, equipped with all the emergency material needed to deal with epileptic seizures and to prevent any damage to the patient (emergency trolley organized according to the treatment of neurological emergencies, antiepileptic drugs).

The occurrence of an epileptic seizure during a TMS experiment does not imply that seizures will reoccur in the future, nor that you should start taking a therapy for the prevention of seizures, nor that we should modify an eventual therapy already underway due to a seizure. The very few cases of TMS-induced seizures described in the literature no longer had episodes later, nor did they report health problems attributable to the event.

Since the TMS produces a magnetic field, people carrying static electric stimulators (e.g. cardiac stimulators, nerve stimulators, auditory implants) that would not work or would be damaged by the magnetic field cannot participate in the study. Also excluded from the examination are the carriers of particular metallic foreign bodies (for splinters, some prostheses, screws and nails) that could move if placed inside the magnetic field. Because the effects of TMS on the developing fetus are not known, pregnant women cannot participate in the study.

ADVERSE EVENT DETECTION:

The Principal Investigator will promptly inform the Local Ethics Committee of the Brescia Hospital of any adverse event incurred during the study.

CLINICA NEUROLOGICA - UNIVERSITA' DEGLI STUDI DI BRESCIA
UO Neurologia 2 - AZIENDA SOCIO SANITARIA TERRITORIALE degli SPEDALI CIVILI DI BRESCIA

Direttore: [name]

REFERENCES

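### Was the figure of 25 subjects calculated for three time points when the written model has four?

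*Combined protocol and SAP*

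**What the plan says.** All of the relevant text is in the combined protocol and SAP.

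- **Sample size (STATISTICAL PLAN).** The inputs are partial eta squared 0.31, f(V) = 0.67, alpha 0.05, power 0.80, two groups and one covariate. The result is that "the sample size expected for two patient groups (real and sham) is 25 total subjects using a repeated-measure ANCOVA study". Enrolment is set at 30, which "would allow monitoring for confounding factors or drop-out patients"; no drop-out rate is given.
- **Efficacy model (same section).** Clinical scores are analysed by a "two-way repeated measure ANCOVA with TIME (T0, T1, T2 and T3) as within-subject factors", with TREATMENT between subjects and "the baseline values of each score as covariate".
- **Test details (same section).** Mauchly's test is planned, and "Greenhouse-Geisser epsilon determination will be used to correct in case of sphericity violation". Post hoc comparisons follow "When a significant main effect was reached".
- **Missing data (same section).** For patients with missing values, "data were assigned using mixed effects models for repeated measures without any ad hoc imputation".
- **Endpoint (END POINTS).** "the primary end point will be the defined as change from baseline in global MRC scores"; no visit is singled out.

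**The concern.** A repeated-measures sample size depends on which effect is tested and on how many measurements enter the test. The sample-size paragraph gives neither, so 25 cannot be checked directly. The label f(V) usually goes with a multivariate test. Solving backwards under that label gives three time levels, whereas the efficacy model lists four visits, T0 to T3.

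If 25 was calculated for the wrong number of levels, the margin of 30 over the requirement would be 1 patient (1/30 = 3.3%) rather than 5 (5/30 = 16.7%), in a disease where the plan itself expects appreciable drop-out. T0 is also both a level of TIME and the covariate, and the text mixes a multivariate effect size with a univariate sphericity correction. A reader could fear that the deciding test is open and that its power varies widely with the choice.

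**Working it through.** **Inputs.** Partial eta squared 0.31, alpha 0.05, power 0.80, two groups, one covariate and N = 30 come from STATISTICAL PLAN. The four TIME levels come from the efficacy model there. The form of the test and the noncentrality formula are assumptions, because the documents give neither.

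**1. Effect size.** f² = 0.31/(1 − 0.31) = 0.4493, so f = 0.670. The printed 0.67 is right.

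**2. Reproducing 25.** Take a multivariate test on m levels with one covariate: df1 = m − 1, df2 = N − 2 − 1 − (m − 1) + 1 = N − m − 1, and λ = f²N. With m = 3 and N = 25, the df are 2 and 21, λ = 0.4493 × 25 = 11.23, and power is 0.803. At N = 24 power is 0.783. Three levels therefore give exactly 25.

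**3. Four levels, same convention, f(V) held at 0.67.**

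| N | df | λ | Power |
|---|---|---|---|
| 25 | 3, 20 | 11.23 | 0.724 |
| 28 | 3, 23 | 12.58 | 0.788 |
| 29 | 3, 24 | 13.03 | 0.806 |
| 30 | 3, 25 | 13.48 | 0.823 |

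The requirement is 29, and 30 meets it.

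**4. Other readings of the same sentence, one covariate.**

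| Reading | N required | Power at 25 |
|---|---|---|
| Univariate partial eta squared, four levels, λ = f²(N − 3)·3ε, ε from 1 down to 1/3 | 13 to 23 | 0.997 to 0.852 |
| TREATMENT, 1 df, λ = f²N | 20 | 0.893 |
| TREATMENT, 1 df, λ = f²(N − 3) | 23 | 0.852 |
| Univariate df with λ = f²Nε, four levels | 26 (ε = 1), 32 (ε = 0.75) | below 0.80 |
| Multivariate, λ = f²·df2, three levels | 29 | below 0.80 |
| Multivariate, λ = f²·df2, four levels | 33 | below 0.80 |

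In the last row, N = 30 gives df2 = 25, λ = 0.4493 × 25 = 11.23 and power 0.742. That formula needs 23, 29 and 33 for two, three and four levels, so it never returns the plan's 25.

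**5. T0 as both level and covariate.** The four-level TIME × TREATMENT contrasts are T1 − T0, T2 − T0 and T3 − T0. With T0 as covariate, subtracting it changes only the covariate's coefficients. The test is therefore the joint 3-df test of the group difference at T1, T2 and T3. On simulated data the two F values agreed to within 1e-13. For this multivariate test, the double use of T0 costs nothing.

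**6. Does the choice of effect leave the trial exposed?** A simulation took 20:10 allocation, correlation 0.7 between visits and a constant benefit of 0.8 SD; the correlation and the benefit are assumptions. Power was 0.815 for the four-level interaction, 0.940 for TREATMENT over T1 to T3, and 0.054 for an interaction restricted to T1 to T3. The low figure is simply alpha, because a constant benefit has no interaction among post-baseline visits. It belongs to a model without T0, which the plan does not specify.

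**7. Drop-out.** For the joint T1 to T3 test with 5 of 30 patients lost, under assumed correlations and effect shapes, simulated power was 0.80 to 0.82 with no loss, 0.72 to 0.81 with loss after T1, and 0.69 to 0.70 if the five gave no data after baseline.

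**The case for a change.** The strongest case for acting is that a sample-size statement should identify its test. f(V) is the plan's own label, the match at three levels is exact, and the written model has four. The plan offers 30 partly as protection against drop-out, so a margin of 1 instead of 5 would be material. Naming the effect and the levels costs only a line of text.

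The omission stands: the effect, the form of the test and the number of measurements are not stated. The inference drawn from it is weaker, for three reasons.

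- The three levels are obtained by back-solving under an assumed formula. The document lists four assessments throughout and names no power program.
- The 29 keeps 0.31 fixed while the test changes. A partial eta squared belongs to the test that produced it, and the documents do not say which pilot test that was. With four levels and N = 25, a value of 0.347 gives 80% power. At N = 30, 0.298 is enough. A small pilot cannot separate such values.
- The margin of 1 counts only patients with no usable data. The plan's mixed model keeps partial follow-up, and the plan never claims a margin of five.

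Nor is there a clean rewording that rescues the three-level figure. If T0 left the TIME factor and TREATMENT were tested jointly with the T1 to T3 interaction, the result would be the same 3-df test as in step 5, needing 29 under the same convention rather than 25. Testing the two separately at 0.05 each gave a simulated type I error of 9.75%.

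**Conclusion.** No change follows. The sample-size paragraph is under-reported, but the documents do not show that 25 is wrong or that it contradicts the four-level model. Under the multivariate convention that reproduces 25, the four-level test needs 29, and the planned 30 gives about 82% power with complete data. If 0.31 is a univariate partial eta squared, which would fit the planned Greenhouse-Geisser correction, or if TREATMENT was powered, 25 is enough.

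The readings that ask for more than 30 (32 or 33) rest on formulas the plan does not give. The 33 comes from a formula that cannot produce its 25.

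The efficacy model already tells an analyst what to fit: four visits, two groups, baseline as covariate, a sphericity correction and mixed models where data are missing. Stating the powered effect and the number of levels would make the calculation easier to check, but it would alter neither N = 30 nor that model.

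This conclusion assumes that the pilot value of 0.31 is taken at face value. The drop-out figures also rest on visit correlations and effect shapes that the documents do not supply.

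### Per-protocol analysis is offered as a remedy for unbalanced drop-out, which it can create or worsen, and the plan does not say whether it or intention-to-treat decides the primary end point

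*Combined protocol and SAP*

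**What the plan says.** Four statements in the combined protocol and SAP bear on this point.

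- END POINTS: "the primary end point will be the defined as change from baseline in global MRC scores". No analysis set is attached.
- STATISTICAL PLAN, drop-out paragraph: "Considering the unneglectable number of drop-out patients, that characterize most trials in ALS", and then "we performed intention-to-treat and per-protocol analysis to reduce any bias due to the possible unbalanced drop-out rates between treatment groups". These two terms appear nowhere else, and neither set is defined.
- Same paragraph, for missing values: "data were assigned using mixed effects models for repeated measures without any ad hoc imputation". The mixed model is not tied to either set.
- STATISTICAL PLAN, clinical scores: "we will use a two-way repeated measure ANCOVA with TIME (T0, T1, T2 and T3) as within-subject factors", with treatment as the between-subjects factor and the baseline score as covariate. No analysis set is named here either.

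No drop-out rate is given, overall or by arm. Allocation is 2:1 (STUDY DESIGN). Stimulation lasts two weeks, and assessments run to six months (PROCEDURES).

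**The concern.** There are three linked faults.

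First, the stated purpose is wrong for one of the two analyses. A per-protocol set is formed by what happens after randomisation. In a progressive disease followed for six months after two weeks of treatment, patients who miss sessions or visits may well be those declining fastest. If one arm loses more of them, its remaining patients look better than the arm as randomised. The analysis then carries the bias that the sentence says it reduces.

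Second, the two analyses are not ranked. If they disagree on global MRC, the plan gives no answer, and either could be reported as the result.

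Third, per-protocol is not defined. It could refer to stimulation sessions received, visits attended or entry criteria met, so the choice stays open until the data are seen.

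At stake is a false benefit, or a masked one, that comes only from who stayed in the analysis.

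**Working it through.** **The plan's own figure.** The plan takes partial eta squared 0.31, so f(V) = sqrt(0.31/0.69) = 0.670, with "considering alpha = 0.05 and the power (1- β) = 0.80". It concludes that "the sample size expected for two patient groups (real and sham) is 25 total subjects using a repeated-measure ANCOVA study". A noncentral F test with lambda = f(V)^2 x N = 0.449 x 25 = 11.2, on 2 and N - 3 = 22 degrees of freedom (two groups, three post-baseline visits), has power 0.805, so 25 is reproduced. The planned 30 leaves 5/30 = 16.7% spare. That is the only drop-out quantity that can be derived from the documents, and it is not split by arm. Everything below therefore rests on assumed rates.

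**Check 1: standardised model, no true effect.** Assumptions: 20 real and 10 sham patients, change-score SD 1, correlation 0.7 between outcome and tendency to stay. If a fraction p of an arm drops out, the mean of those retained rises by 0.7 x phi(z_p)/(1 - p), where phi is the normal density and z_p the p-quantile.

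- p = 10%: 0.7 x 0.1755/0.9 = 0.137
- p = 20%: 0.7 x 0.2800/0.8 = 0.245
- p = 30%: 0.7 x 0.3477/0.7 = 0.348
- p = 40%: 0.7 x 0.3863/0.6 = 0.451

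The bias is the real-arm value minus the sham-arm value. Type I error is from simulation (20,000 runs, two-sided t test at 0.05).

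| Lost, real / sham | Bias after exclusion (SD) | Type I error after exclusion |
|---|---|---|
| 30% / 10% | 0.348 - 0.137 = +0.21 | 0.087 |
| 40% / 10% | 0.451 - 0.137 = +0.31 | 0.121 |
| 10% / 30% | 0.137 - 0.348 = -0.21 | 0.073 |
| 20% / 40% | 0.245 - 0.451 = -0.21 | 0.073 |
| 20% / 20% | 0.00 | 0.051 |

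The all-randomised comparison shows no bias and an error of about 0.05. It was given complete outcomes, which real drop-outs would not supply, so it is a benchmark and not a forecast.

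**Check 2: MRC scale, no true effect.** Assumptions: mean decline 1.5 points per month, SD of individual slopes 0.75 to 1.5, measurement error SD 2, and log-odds of leaving before T3 rising by 1.5 per SD of faster decline. The analysis is an ANCOVA of T3 change in completers, adjusted for T0, with 4,000 trials per scenario. Completers stand in for the undefined per-protocol set.

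| Scenario | Completer bias, real minus sham (MRC points) |
|---|---|
| 25% real, 10% sham lost | about +0.7 to +1.4 |
| 10% real, 30% sham lost | about -0.9 to -1.9 |
| 20% lost in each, decline-related in real arm only | about +1.0 to +2.0 |
| 20% lost in each, same mechanism | about 0 |

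The standard error of the estimate is 2.1 to 4.0 points. The bias in the first three rows is thus about one third (0.7/2.1 = 0.33) to one half (2.0/4.0 = 0.50) of a standard error.

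**Check 3: no deciding analysis.** If significance in either analysis counted as success, type I error would be about 0.07 to 0.10 in the MRC-scale model. In the standardised model it is 0.073 to 0.078 when drop-out is unrelated to outcome, and 0.076 to 0.113 when it is related. The lack of a ranking therefore matters even if drop-out is uninformative.

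**Check 4: what remains after the fix.** In the MRC-scale model, an all-randomised estimate that uses T0 to T2 data under missing-at-random still carries about +0.5 to +0.6, -0.6 to -0.9 and +0.7 to +0.8 points in the three biased scenarios. That is 41% to 72% of the completer bias. It remains because leaving depends on the true slope, which the observed visits show only in part.

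**The case against.** The strongest defence is that the plan already has a sound drop-out measure. Intention-to-treat is named first, and the next sentence handles missing values with a mixed model and no ad hoc imputation, which is valid under missing-at-random. Running both sets can also be read as a check for agreement. This stands in part: the materials for a good primary analysis are in the document. But the mixed model is attached to neither set, it cannot restore patients whom a per-protocol set has removed, and nothing ranks the two results.

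The sizes are also modest and rest wholly on assumptions. The simulation uses a T3 completer ANCOVA, which is neither the plan's repeated-measures ANCOVA nor its mixed model. That limits the figures to illustration. It does not touch the missing ranking or the wrong rationale.

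Some stronger readings are tempting, and the documents do not support them.

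- *That per-protocol exclusion always biases the comparison.* It does so only when exclusion is related to outcome and differs by arm.
- *That per-protocol means attending the six-month visit.* A reader might infer this because the sentence is about drop-out, but the document does not define the set.
- *That chance imbalance in drop-out between small arms shows bias.* With about 10 sham patients, one patient is 10 percentage points. When the mechanism is the same in both arms, the average bias is about nil.
- *That the sponsor means to choose the more favourable result.* Nothing shows such an intention.

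**Conclusion.** The point holds. The plan gives per-protocol analysis a bias-reducing role that it cannot fill, leaves both sets undefined, and names no deciding analysis for global MRC. This follows from the text alone and can be stated with high confidence.

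The size is less certain. With 20:10 patients and the assumed decline and drop-out, completer-only bias is about 0.7 to 2.0 MRC points in absolute size when drop-out is unbalanced or decline-related in one arm only. Taking either result as success moves type I error from 0.05 to about 0.07 to 0.10. This is a moderate distortion in a small trial. It justifies a change of wording and does not call for a change of design.

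**What to change.** Replace the sentence on the two analyses with:

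> The conclusion on global MRC rests only on the intention-to-treat set (all randomised patients, as randomised, all available visits), analysed with the mixed-effects model for repeated measures already named, and not with a repeated-measures ANCOVA that drops patients with a missing visit. The per-protocol analysis is supportive, is not a remedy for unbalanced drop-out, and cannot change the conclusion.

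Define the per-protocol set before unblinding by stimulation sessions received and absence of entry violations, not by attendance at T2 or T3. A fully treated patient who leaves later then stays in, with the visits they have.

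Amend the clinical-scores paragraph to match. A conventional repeated-measures ANCOVA needs every visit, so an analysis labelled intention-to-treat could otherwise still be an analysis of completers.

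The cost is SAP wording; design, patient numbers and data collection do not change. The downside is that a per-protocol result can no longer decide the trial. The change reduces drop-out bias under missing-at-random, but it does not remove bias from drop-out that depends on unobserved decline, and the report should say so.
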